## 9.2 Analysis Population

All the data collected up to the point of the explant or expirations will be included in the safety and effectiveness analyses. The primary safety analysis will include all the enrolled subjects. The primary effectiveness analysis will include the subjects who survived and have NYHA assessment at 8 years post implant.

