#### 6.1.2 Late Post-Operative Follow- Up

Postoperative follow-up visits are required between 3-6-months, at one year, and annually thereafter for a minimum of 8 years. Required evaluations and data requirements are listed below in Table 8.

Table 8. Late Post-Operative Procedures a	and Data Requirements
---	-----------------------

Patient Status	Visit Date, Type of Visit
----------------	---------------------------

Physical Assessment	Heart Rate, Blood Pressure, NYHA classification		
Electrocardiogram	Cardiac Rhythm		
Blood studies	RBC, WBC, HCT, Plasma Free HGB (or Haptoglobin and SLDH), Platelet and Reticulocyte counts		
Medication Use	Antiplatelet, Antithrombolytic Therapies		
Coagulation Profile	PTT or INR		
Echocardiography (6 mo, 1. 2, 4 6, and 8 year follow-up visits)	Exam Date/Interval, clinical evidence of PV leak or regurgitation		
Echo Core Lab	Cardiac output, Ejection fraction, Peak and mean valve gradients, assessment of stenosis or regurgitation, LV structure and function, LV mass, jet velocities		
Quality of Life Survey (6 month visit only)	EQ-5D		
Adverse Events	All adverse events or complications that have occurred since the last visit		

Echocardiography exams are required at the 6-month visit (between 3-6 months), and at 1, 2, 4, 6, and 8 year follow-ups ( $\pm$  1 month). A QOL survey (EQ-5D) will be completed for the 6-month follow-up visit.

Use of anticoagulant therapy is recommended for two to three months postoperatively except where contraindicated. The appropriate anticoagulation therapy must be determined by the physician on an individual basis and based on current ACC/AHA guidelines.

Clinical assessment of adverse events shall be conducted per revised STS guidelines (Appendix 1) and reported per the event classifications and definitions provided in Section 7.0 and Appendix 8 respectively.

This document and the information contained herein is considered Proprietary and Confidential and may not be reproduced, used or disclosed without written permission from Edwards Lifesciences LLC.

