#### 6.8 Valve Explants

Every effort should be made to return the explanted valve(s), at autopsy or explantation to Edwards. The explanted valve should be placed in a container with a suitable histological fixative such as 10% formalin or 2% glutaraldehyde immediately after excision and returned to Edwards. Refrigeration is not necessary under these circumstances. Contact Edwards Clinical Research for additional instructions.

Any pertinent information, e.g. operative notes, autopsy report etc should be sent to Edwards. All supporting data should be de-identified at the site to protect the privacy of the study subject.

This document and the information contained herein is considered Proprietary and Confidential and may not be reproduced, used or disclosed without written permission from Edwards Lifesciences LLC.

After the study valve is explanted, the subject will be followed for either an additional 30 days to monitor for any new adverse events or until all study device related serious adverse events are resolved. After that point the subject will be discontinued from the study. No further evaluations and/or case report forms are needed after study exit. Data from these subjects will be included in analysis

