#### 6.9 Deaths/Autopsy Reports

All deaths that occur during study participation and deaths that occur 30 days post-study valve explantation shall be reported to the Edwards Clinical Affairs Department. The Investigator shall provide a written summary of the subject death including the cause of death and relationship of the death to the study valve or procedure. Copies of an autopsy report and/or death certificate shall be submitted to Edwards as permitted by local law. Death notifications shall be de-identified in order to protect the privacy of the subject.

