#### 9.4.2 Time to Death, Reoperation, and Explant

Time to death from the date of operation will be analyzed by the method of Kaplan and Meier. Time to reoperation from the date of operation as well as time to explant from the date of reoperation will be similarly analyzed. For time to explant and time to reoperation, the time to *first* explant or reoperation will be calculated for those subjects requiring explant or reoperation. These analyses will also be reported for the entire study cohort and also stratified by valve size and valve model. Analyses for time to explant and time to reoperation will also be stratified by fatal versus non-fatal events.

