#### **Valve-Related Mortality**

Valve-related mortality is any death caused by structural valve deterioration, nonstructural dysfunction, valve thrombosis, embolism, bleeding event, or operated valve endocarditis; death related to reintervention on the operated valve; or sudden, unexplained death. Deaths caused by heart failure in patients with advanced myocardial disease and satisfactorily functioning cardiac valves are not counted. Specific causes of valve-related deaths should be reported.

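### Section 9.2 takes data up to explant with no exception for death endpoints, which conflicts with Sections 6.8, 6.9, 9.4.2 and Appendix 1; read literally, it leaves out deaths after the explant operation

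*Combined protocol and SAP*

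**What the plan says.** Section 9.2 (Analysis Population) holds the only general rule in Section 9 on which data enter the analyses: "All the data collected up to the point of the explant or expirations will be included in the safety and effectiveness analyses". It draws no distinction between endpoints. Section 3.3.2 lists death and valve-related death among the secondary safety endpoints.

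Five other places bear on what happens after explant:

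- Section 6.8 (Valve Explants): after explant "the subject will be followed for either an additional 30 days to monitor for any new adverse events", or until device-related serious adverse events have resolved, and then leaves the study. The section closes with "Data from these subjects will be included in analysis".
- Section 6.9 (Deaths/Autopsy Reports): "All deaths that occur during study participation and deaths that occur 30 days post-study valve explantation shall be reported", with the investigator's view of the relationship to the valve or procedure.
- Section 9.4.2: time to death runs from the operation by Kaplan-Meier, with no censoring at explant mentioned. Time to explant and time to reoperation are also to be "stratified by fatal versus non-fatal events".
- Appendix 1, Valve-Related Mortality: the definition includes "death related to reintervention on the operated valve". Section 6.1.2 makes this guideline the basis for clinical assessment of adverse events.
- Appendix 1, Valve Outcome Versus Patient Outcome: explant ends observation for valve performance, whereas patient outcome runs to death or censoring.

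**The concern.** Take a subject whose valve fails at year 6 and who dies four days after it is replaced. Sections 6.8 and 6.9 collect that death, and Appendix 1 counts it as valve-related if it is related to the reintervention. Under a literal reading of Section 9.2, the subject's data stop at the operation. The subject is then censored alive, and the death reaches neither the mortality rates nor the survival curve.

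The deaths at issue follow directly from removal of the study valve, so leaving them out is not neutral. Omission can lower the death counts but never raise them, and it censors subjects just as their risk is high. In a study of long-term safety, the rule for these deaths should be settled before the analyst meets them.

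**Working it through.** **The texts side by side.** For a death inside the post-explant follow-up:

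| Source | Does the death count? |
|---|---|
| 9.2, read literally | No: the data end at explant |
| 6.8 | Yes, on its natural reading: explanted subjects' data are included, stated directly after the follow-up is described |
| 6.9 | Collected, with relationship to valve or procedure |
| 9.4.2 | Yes, by implication: no censoring of death at explant, and fatal explants are to be identified |
| Appendix 1 | Yes, and valve-related if related to the reintervention |

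Appendix 1 uses explant as the end point for valve performance only. Section 9.2 states one cut for all safety and effectiveness analyses.

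**Size.** The plan gives no figure for this point, so there is none to reproduce. The inputs for an illustration are the late events for the predecessor valves (model 7300TFX Instructions for Use in Appendix 4, Tables 1 and 2) and the 808 subject-years in Section 9.1.

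Rate = late events / late patient-years:

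- Model 6900 explants: 8 / 1072.5 = 0.75% per year (printed 0.7).
- Model 6900P explants: 8 / 856.24 = 0.93% per year (printed 0.9).
- Model 6900 valve-related deaths: 16 / 1072.5 = 1.49% per year (printed 1.5).
- Model 6900P valve-related deaths: 12 / 856.24 = 1.40% per year (printed 1.4).

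Expected events at 808 subject-years = 808 × unrounded rate:

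- Explants: 6.0 (6900) and 7.5 (6900P).
- Valve-related deaths: 12.1 (6900) and 11.3 (6900P).

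Deaths omitted = explants × 30-day mortality after explant. The documents do not give that mortality, so 5 to 15% is an assumption:

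- Low end: 6.0 × 5% = 0.3 deaths; 0.3 / 12.1 = 2.5% of valve-related deaths.
- High end: 7.5 × 15% = 1.1 deaths; 1.1 / 11.3 = 10%.

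At 20%, the counts would be 1.2 (6900) and 1.5 (6900P). More subject-years raise the counts in proportion and leave the percentages unchanged.

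**What does not move.** The four primary safety tests use thromboembolism, hemorrhage, perivalvular leak and endocarditis. The primary effectiveness test uses NYHA class. Neither these tests nor the enrolment figure of 250 depends on how a post-explant death is counted.

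**The case against.** A reader might infer that the plan definitely discards these deaths, that valve-related mortality will therefore be understated, and that the fatal stratum in Section 9.4.2 cannot be filled. The documents do not go that far.

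- Section 9.2 is a sentence of inclusion. It does not say that later data are excluded or that subjects are censored alive at explant. Those are inferences from where the sentence stops.
- The more specific sections favour inclusion. An analyst could reasonably let Sections 6.8 and 9.4.2 govern over the general sentence.
- The fatal stratum is not empty even under the cut. Fatal reoperations without explant are untouched. An intraoperative death coincides with the explant, so Section 9.2 is ambiguous for it. The adverse event form in Appendix 5 records an event's onset separately from an outcome of death and its date, so an explant dated at surgery can still be classed as fatal.
- Stopping at explant is right for valve-performance endpoints and agrees with Appendix 1.
- The effect is about one death or fewer at 808 subject-years under the 5 to 15% assumption, on secondary endpoints with no stated success threshold.

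All of this stands, and it limits the point to an unresolved conflict. It does not remove the conflict. If Section 9.2 is only permissive, no general rule says whether a post-explant death counts, and the choice falls to the analyst. If it is a cut, it contradicts four other parts of the document. Either way the same clarification is needed.

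**Conclusion.** The point holds as a contradiction to be reconciled, with a one-directional bias if Section 9.2 is followed as written. It is not established that deaths will be dropped. On the literal reading, about 0.3 to 1.1 deaths would be omitted at 808 subject-years, or roughly 2.5 to 10% of the 11.3 to 12.1 expected valve-related deaths. That rests on predecessor rates carrying over to the study valves and on the assumed 5 to 15% mortality. The percentages also treat every omitted death as valve-related and take the predecessor count as the base, although the documents do not say whether that count already includes post-explant deaths.

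Only secondary safety endpoints are affected. The change should be made because it is specific and the data are already required. It does not threaten the study's primary conclusions.

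**What to change.** Amend Section 9.2 to give two rules:

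1. For valve-performance endpoints (thromboembolism, hemorrhage, perivalvular leak, endocarditis, structural deterioration, hemodynamics and NYHA class), data run to explant or death, as now.
2. For death, valve-related death and the fatal/non-fatal split of explant and reoperation, deaths are counted through the end of the post-explant follow-up in Section 6.8, with valve-relatedness assigned by the Appendix 1 definition.

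Add a cross-reference in Section 9.4.2 so that the survival analysis and the fatal stratum use the second rule. Where a death rate is linearized, the follow-up time after explant should enter the denominator. At 7.5 explants and 30 days each, this is 7.5 × 30 / 365.25 = 0.6 subject-years, which is negligible against 808.

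The cost is a few sentences. Sections 6.8 and 6.9 already require the follow-up and the death reports, so no new data are needed. The downside for the sponsor is that reported valve-related mortality may rise slightly.

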## 9.3 Safety Analysis

## 9.3.1 Primary Safety Endpoint

As described above a statistical test based on the Poisson distribution will be performed to investigate whether the linearized yearly rate for each

This document and the information contained herein is considered Proprietary and Confidential and may not be reproduced, used or disclosed without written permission from Edwards Lifesciences LLC.

cardiovascular adverse event (thromboembolism, all hemorrhage, all perivalvular leak, and endocarditis) is less than 2 times the appropriate Objective Performance Criteria from Annex R, Table R.1 per ISO 5840 as proposed by the US FDA in the Heart Valve Guidance draft 2009.

For reporting purposes, the percent of subjects who experience an early adverse events within 30 days of implant will be summarized. Linearized rates will be used to summarize adverse events for the late (>30 days) post-operative period. The linearized rates will be reported as the number of events occurring after the early post-operative period per year of subject survival. In addition, the linearized rate and 30-day frequency for thromboembolism will be stratified by concomitant cardiac problems (atrial fibrillation, sinus rhythm, pacemakers, etc.).

Accounting for both early and late post-operative events, actuarial analysis according to Kaplan-Meier will be used to show estimated probability of freedom from each adverse event.

## 9.4 Secondary Safety Endpoints

The analysis of secondary safety endpoints will be presented for the entire study cohort and also stratified by valve size according to the Tissue Annulus Diameter (TAD) and by valve model (7000/7000 TFX, 7200 and 7300/7300TFX).

#### 9.4.1 Blood Data

Blood data (red blood count, white blood count, hematocrit, plasma free hemoglobin (or Haptoglobin and SLDH), reticulocyte and platelet counts) will be collected preoperatively, at 6-months and annually post implant. This blood data will support the absence / presence of related adverse events; in particular hemolysis. Data will be reported as the percent of subjects with results within the normal ranges at each time interval. The percent of subjects with hemolysis at

This document and the information contained herein is considered Proprietary and Confidential and may not be reproduced, used or disclosed without written permission from Edwards Lifesciences LLC.

each point will also be reported. Summaries will be presented for the entire study cohort and will also be stratified by valve size and valve model.

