# 6.0 STUDY PROCEDURES

Edwards will provide the study sites with the post approval study clinical protocol, case report forms (CRFs) (Appendix 5), Quality of Life survey (Appendix 6) and all other necessary study related documentation. Edwards' Clinical Affairs Department or authorized designee will conduct all aspects of data quality assurance (data monitoring, and monitoring of study sites) per departmental Standard Operating Procedures.

Each study site will adhere to all the requirements specified in this protocol. Assessments will be obtained for the preoperative and operative visits, and postoperatively at discharge, six months, 1-year and annually thereafter for a minimum of 8 years (see Tables 4, 5, 6 and 7).

The investigator will make every attempt to follow the subjects and will document the information gathered during the required study follow-up visits on the standardized CRFs. The subjects will be encouraged by the investigator to report any address or telephone number changes. They will also be informed of the importance of returning for scheduled follow-up visits even if they are not having any problems.

Each site will provide a list of normal blood values and a certificate, or equivalent documentation, outlining the quality level of their laboratory prior to study initiation.

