## 9.5.2 Hemodynamic Performance

Echocardiography data will be obtained preoperatively, early postoperatively and/or discharge, at 6-months and at 1, 2, 4, 6 and 8 year follow-ups. Descriptive statistics for the continuous echo variables and change from baseline (e.g. mean, standard deviation, and range) will be categorized by time interval and valve size. Regurgitation data will be summarized using frequency at each severity level by time interval and valve size. Improvement in regurgitation at one year will be analyzed via the Jonckheere-Terpstra test. Change at one year from baseline for all other hemodynamic outcomes will be analyzed using paired *t*-tests. These analyses will also be reported for the entire study cohort and also stratified by valve model.

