#### STUDY NUMBER 2006-05 CARPENTIER-EDWARDS PERIMOUNT MAGNA MITRAL EASE

COMPLETE EITHER B OR C       WITHIN NORMAL       IF NO, CLINICALLY         BLOOD PARAMETER       VALUE       UNITS       RANGE?       SIGNIFICANT?         PLASMA FREE       (mg/dL)	COMPL							
B.       VALUE       UNITS       WITHIN NORMAL       IF NO, CLINICALLY         BLOOD PARAMETER       Image: Significant?       Significant?         PLASIMA FREE       (mg/dL)       Image: Significant?         PLASIMA FREE       (mg/dL)       Image: Significant?         OR       Value       UNITS       WITHIN NORMAL       IF NO, CLINICALLY         BLOOD PARAMETER       Value       UNITS       WITHIN NORMAL       IF NO, CLINICALLY         BLOOD PARAMETER       Value       UNITS       RANGE?       Significant?         BLOOD PARAMETER       Value       UNITS       RANGE?       Significant?         BLOOD PARAMETER       Value       UNITS       RANGE?       NO         BLOOD PARAMETER       Value       UNITS       RANGE?       NO         SERUM LDH       (mg/dL)       Image: Significant?       Image: Significant?         SERUM LDH       (U/L)       Image: Significant?       Image: Significant?         ELEVATED SERUM LDH - FRACTIONED       Image: Significant?       Image: Significant?         ELEVATED SERUM LDH - FRACTIONED       Image: Significant?       Image: Significant?         PREGNANCY TEST       Image: Significant?       Image: Significant?         Not Done (complete Protocol Deviation)		ETE EITHER B	OR C					
BLOOD PARAMETER       VALUE       UNITS       RANGE?       SIGNIFICANT?         PLASMA FREE       (mg/dL)	В.				WITHIN N	ORMAL	IF NO, C	
PLASMA FREE       NO       YES       NO         PLASMA FREE       (mg/dL)	BLOO	D PARAMETER	VALUE	UNITS	RANG	SE?	SIGNII	FICANT?
Instruct       (mg/dL)       Image: Construct of the second secon	DLASK				YES	NO	YES	NO
OR         C.       VALUE       WITHIN NORMAL       IF NO, CLINICALLY         BLOOD PARAMETER       VIEW       NO       YES       NO         HAPTOGLOBIN       (mg/dL)       Image: NO       YES       NO         SERUM LDH       (U/L)       Image: Image: NO       Image: NO       Image: NO         ELEVATED SERUM LDH - FRACTIONED       Image: I	HEMO	GLOBIN		(mg/dL)				

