#### COMPLETE SECTION B OR C

В.			WITHIN	NORMAL	IF NO, CLINICALLY				
BLOOD	VALUE	UNITS	RANGE? SIGNIFICAN			FICANT?			
PARAMETER			YES	NO	YES	NO			
PLASMA FREE HEMOGLOBIN		(mg/dL)							

White and Yellow: Return to Edwards Lifesciences, Clinical Affairs Pink: Retain for your Records

PROPRIETARY DATA: THIS DOCUMENT AND INFORMATION CONTAINED HEREIN MAY NOT BE REPRODUCED, USED, OR DISCLOSED WITHOUT WRITTEN PERMISSION OF EDWARDS LIFESCIENCES, HEART VALVE THERAPY GROUP, CLINICAL AFFAIRS ASSESSMENT DATA REV E 20110526

	Clinical Review:		Data Management:		
FOR	First Review:	Second Review: (optional)	First Data Entry:	Second Data Entry:	Subevent #
EDWARDS	By:	By:	By:	By:	(optional)
USE ONLY	Date:///	Date://	Date://	Date://	

Patient Study ID # 2 0 0 6 0	5									Clinic #
ASSESSMENT DATE:	D	D	М	М	М	Y	Y	Y	Y	I

OR

C. BLOOD	VALUE	UNITS	WITHIN N RANG	ORMAL GE?	IF NO, CLI SIGNIFI	NICALLY CANT?
PARAMETER			YES	NO	YES	NO
HAPTOGLOBIN		(mg/dL)				
SERUM LDH		(U/L)				

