		Heparin Induced Thrombocytope nia (HITS)	HITS is diagnosed when thrombocytopenia (defined as >50% of the baseline value or a low platelet count between 20–100 × 10^9/liter) is reported caused by administration of various forms of heparin. HITS must be confirmed by a Heparin Assay and or D-Dimer laboratory test.	Not defined

		7		
		Other Coagulopathy	Coagulopathy other than DIC or HITS confirmed by laboratory tests.	Not defined
	Hematoma		Collection of blood (or its degradation products) which exceeds 5 cm in diameter, requires treatment or prolongs hospitalization.	Not defined
		Specify site		
	Hemolysis		The destruction of red blood cells, caused by disruption of the cell membrane and resulting in the release of hemoglobin. The clinical diagnosis is made by the measurement of plasma free hemoglobin.	Not defined
	Hemolytic Anemia		Anemia due to hemolysis, either in the blood vessels (Intravascular hemolysis) or elsewhere in the body (extravascular).	Not defined
		Mechanical hemolytic anemia (extravascular)	A form of hemolytic anemia due to mechanically induced damage to red blood cells. Red blood cells, while flexible, may in some circumstances succumb to physical shear and compression. A common form, called microangiopathic hemolytic anemia , is a chronic condition due to prosthetic heart valves.	Not defined
	GI Bleed	General Def	Detection or frank blood or hemoglobin in the GI tract documented by diagnostic test or laboratory results that causes death, hospitalization, or permanent injury (eg, vision loss) or necessitates transfusion. Refer to definition of "Bleeding Events" for reportability.	Not defined
		Upper	Detection of frank blood or hemoglobin in the upper gastrointestinal tract confirmed by diagnostic or laboratory test result.	Not defined
		Lower	Detection of frank blood or hemoglobin in the stool documented by hemmocult test or other diagnostic procedure.	Not defined
	Intracranial Bleed		Includes all bleeding within the cranium either subarachnoid, intra-parenchymal, or intracerebral requiring treatment or resulting in neurological deficit. Bleeding related neurological events should be captured as bleeding complications (See Bleeding) while embolic related deficits should be recorded as embolic events.	Not defined

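### Section 9.4.1 reports blood results only as percent in range, which merges low with high and makes no comparison with each subject's preoperative result (minor, cheap to improve)

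*Combined protocol and SAP*

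**What the plan says.** Section 9.4.1 (Blood Data) covers red and white cell counts, hematocrit, plasma free hemoglobin (or haptoglobin and LDH), reticulocytes and platelets, taken preoperatively, at 6 months and annually. Its stated purpose is: "This blood data will support the absence / presence of related adverse events; in particular hemolysis". Section 8.2 (Minimization of Risks) adds anemia to that purpose. The planned summary of the values is: "Data will be reported as the percent of subjects with results within the normal ranges at each time interval". Hemolysis is also tabulated at each point, as a percentage of subjects. Both summaries are given for the whole cohort and by valve size and model.

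Neither Section 9.4.1 nor any other section plans a split of out-of-range results into low and high, a change from the preoperative value, or a shift table for blood. By contrast, Section 9.5.2 plans "Descriptive statistics for the continuous echo variables and change from baseline".

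Three collection details matter:
- The case report forms in Appendix 5 record the numeric value, an in-range yes/no box and, under "IF NO, CLINICALLY", a yes/no box for clinical significance. They have no field for range limits and no low/high flag.
- For the hemolysis markers, the follow-up form instructs "COMPLETE SECTION B OR C", meaning plasma free hemoglobin, or haptoglobin with LDH.
- Section 6.0 states: "Each site will provide a list of normal blood values and a certificate". These are due before the study starts at the site.

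**The concern.** Two pieces of information are lost when a laboratory value becomes in range or not in range, counted visit by visit.

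The first is direction. Haptoglobin, hematocrit and red cells worsen downward in hemolysis or anemia, but they can also be high. If some subjects move from high to normal while others move from normal to low, the two movements offset each other in the reported percent.

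The second is pairing. The preoperative percent may appear as one of the time intervals, so a reader could compare two columns. Two columns do not show how many subjects who were normal before surgery became abnormal after it.

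What is at stake is how well a supportive safety table serves its stated purpose. No primary test, error rate or sample size depends on it.

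**Working it through.** The plan gives no figure to reproduce here, so the check has three parts.

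**1. Text.** The passages on blood data (Sections 3.3.2, 6.0, 6.1, 8.2 and 9.4.1), the forms in Appendix 5, and Sections 9.5.2 and 9.7 were read for any directional or paired blood summary. There is none. Change from baseline is planned only for echo variables.

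**2. Pairing, with no distribution assumed.** Take N paired subjects with the same proportion p in range at both visits. The number moving from normal to abnormal must equal the number moving back, so it can lie anywhere from 0 to min(pN, (1−p)N). With assumed N = 100:
- 90% and 90%: 0 to 10 subjects newly abnormal.
- 80% and 80%: 0 to 20.
- 60% and 60%: 0 to 40.

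In the 80% case the 20 out-of-range results could be all low, all high or any mix, and the reported percent would be the same.

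**3. Direction, under an assumed model.** The documents give no distribution of blood values. The assumptions are normal values, a normal range of ±1.96 SD, and a fall of s SD in every subject from a preoperative mean d SD above the centre of the range. With m the current mean:
- in range = Φ(1.96 − m) − Φ(−1.96 − m)
- low = Φ(−1.96 − m)
- before surgery m = d; afterwards m = d − s.

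| Start d (SD) | In range, before → after 1 SD fall | Low, before → after 1 SD fall | In range, before → after 0.5 SD fall |
|---|---|---|---|
| −1 | 83.0 → 48.4% | 16.9 → 51.6% | 83.0 → 67.7% |
| −0.5 | 92.1 → 67.7% | 7.2 → 32.3% | 92.1 → 83.0% |
| 0 | 95.0 → 83.0% | 2.5 → 16.9% | 95.0 → 92.1% |
| +0.25 | 94.3 → 88.3% | 1.4 → 11.3% | 94.3 → 94.3% |
| +0.5 | 92.1 → 92.1% | 0.7 → 7.2% | 92.1 → 95.0% |
| +1 | 83.0 → 95.0% | 0.2 → 2.5% | not computed |

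The percent in range changes by less than 5 points for starts from +0.29 to +0.71 SD (1 SD fall) or from −0.17 to +0.67 SD (0.5 SD fall). From starts above those bands, a fall reads as improvement.

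The +0.5 SD row is the exact-cancellation case, because the low and high tails exchange places. Applied to the 101 subjects planned at 8 years, low results go from 0.007 × 101 ≈ 0.7 to 0.072 × 101 ≈ 7.3.

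A marker judged only against an upper limit would not be masked: a 1 SD rise from the centre takes the percent in range from Φ(1.96) = 97.5% to Φ(0.96) = 83.1%.

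**The case against.** The strongest reply is that the stated purpose is met elsewhere. Hemolysis is reported as a percent at each point and has its own linearized and actuarial analysis (Section 3.3.2). All adverse events are reported regardless of cause and reviewed by a Clinical Events Committee (Sections 7.0 and 8.2.2). Each out-of-range value prompts a clinical-significance judgement. Plasma free hemoglobin, the diagnostic marker, worsens upward, so its rise would show. Percent in range is also a reasonable common scale when values come from local laboratories, whereas the echo data are read centrally.

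Most of this stands, and it limits the point to a minor one. It does not remove it. These safeguards catch diagnosed events, but they supply neither direction nor within-subject movement. Section 9.4.1 does not say the significance box will be tabulated, and the box is not completed for in-range results. Appendix 8 says of hemolysis: "The clinical diagnosis is made by the measurement of plasma free hemoglobin". Sites that use haptoglobin and LDH need not record that marker, so low haptoglobin is an important signal there, and the planned table cannot separate it from high haptoglobin. Low/within/high counts keep the same common scale across laboratories.

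A reader might infer three stronger things that the documents do not support:
- That hemolysis would be hidden. Diagnosed hemolysis has its own analyses.
- That data from explanted or deceased subjects are lost. Section 9.2 says "All the data collected up to the point of the explant or expirations will be included in the safety and effectiveness analyses".
- That the illustration can be scaled to 250 subjects. That is the minimum enrolment, not a follow-up count: Section 4.2 records 55 subjects no longer available by November 2013, and 101 are planned at 8 years.

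**Conclusion.** The point holds as a minor, cheap improvement to a secondary descriptive table. It is not an error in the plan. That blood results are summarised without direction or pairing follows from the text alone and needs no model.

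How much this would obscure is not known. The normal model, the uniform fall and the ±1.96 SD range are all assumptions, and the example of 0.7 to 7.3 low results among 101 is the case of perfect cancellation. From a low or centred start, a 1 SD fall would be plain in the planned table, without its direction. The documents do not show that masking will occur in this study.

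**What to change.** Replace the percent-in-range sentence in Section 9.4.1 with wording such as:

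*For each blood parameter and visit, the number assessed and the number and percent below, within and above the site's normal range will be reported for the whole cohort, with a shift table from the preoperative category (low, normal, high) to the category at that visit. Shift tables for hemolysis markers will be made per marker (plasma free hemoglobin, or haptoglobin and LDH) among subjects with the same marker at both visits, showing the paired number. Low and high will be derived from the recorded value, the in-range box and the site's normal values.*

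Keep the percent-with-hemolysis sentence. Paired numeric change and a count of results marked clinically significant are optional additions.

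No new blood draw, visit or form is needed. The costs are:
- extra tables;
- linking site reference ranges, since the forms have no limit fields and the lists are supplied before initiation for follow-up of at least 8 years;
- smaller paired numbers for the either/or markers, and small cells by valve size and model, which is why whole-cohort presentation is proposed;
- the route for the change. Under Section 10.7, protocol changes need a written amendment agreed by FDA and then IRB or ethics committee approval. The wording could be carried in an amendment, or the tables could be added as supplementary tables at reporting.
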